Study Protocol:

Sreamlining Management And Rehabilitation with Technology for ankle fractures: The (SMART-Ankle) feasibility study

Version 1.3 August 2022

Author/s:

[name]

[name]

[name]

Sponsor:

RBWH

CONFIDENTIAL

This document is confidential and the property of the Jamieson Trauma Institute. No part of it may be transmitted, reproduced, published, or used without prior written authorisation from the institution.

Statement of Compliance

This document is a protocol for a research project. This study will be conducted in compliance with all stipulation of this protocol, the conditions of the Royal Brisbane and Womens Hospital Ethics Committee approval, the NHMRC National Statement on ethical Conduct in Human Research (2007), the Australian Conde for Responsible Conduct of Research, the Note for Guidance on Good Clinical Practice (CPMP/ICH-135/95) and the Code of Practice for the Exposure of Humans to Ionizing Radiation for Research Purposes (2005).

Contents

GLOSSARY OF ABBREVIATIONS & TERMS	3
SYNOPSIS	3
1. Background	4
2. Study Methods	5
2.1 Brief summary	5
2.2 Study Design	6
2.3 Interventions	6
2.4 Sample Size	6
2.5 Patient population	6
2.6 Participant Recruitment	6
2.7 Study Eligibility	6
2.7.1 Inclusion criteria	7
2.7.2 Exclusion criteria	7
2.8 Study Intervention	8
2.9 Immediate postoperative care	9
2.10 Use of Smart device during postoperative rehabilitation	9
3.0 Outcome measures	9
3.1 Magnes Device specific Outcome Measures	9
Aim 1:	9
Aim 2:	10
Aim 3:	10
3.2 Baseline Assessment	11
3.2.1 Assessment 2	11
3.2.2 Final appointment	11
4.0 Data collection	12
4.1 Data management	13
5.0 Withdrawal or dropout from study	13
6.0 Risks and Benefits	13
7.0 Contacts and locations	14
References	15
APPENDIX 1: Rehabilitation protocol	16
APPENDIX 2: Rehabilitation timeline	23
APPENDIX 3: Charlson Comorbidity Questionnaire	24

GLOSSARY OF ABBREVIATIONS & TERMS

Abbreviation	Description (using lay language)
RBWH	Royal Brisbane Womens Hospital
JTI	Jamieson Trauma Institute
SMART	Streamlining Management And Rehabilitation with Technology
GDPR	General Data Protection Regulation

SYNOPSIS

Full Title	Streamlining Management And Rehabilitation with Technology for Ankle Fractures
Short title	SMART Ankle Feasibility Study
Study design	Single group prospective cohort study
Sites	1
Expected sample size	12
Recruiting time period	6 months
Study aim	To evaluate whether patients can use these devices during rehabilitation and whether the data from the device enhances clinical outcomes
Inclusion criteria	18 years and older Ankle fracture as per protocol Charlson Comorbidity Scores of <4 Can stand and use crutches post operatively Can attend outpatient follow up visits at RBWH
Exclusion criteria	Charlson Comorbidity Index score ≥ 5

Primary objective	Feasibility for patients to use the Magnes device
Secondary objectives	Clinical relevance of the data from the device
Outcome measures	Weight bearing characteristics of patients who have undergone surgical fixation of their ankle fracture for 12 weeks EQ-5D 5L AFORM Questionnaire

1. Background

Ankle fractures is one of the most common lower limb fracture and lead to important limitations in activities and adverse events (1). Available trauma statistics for the period 2015 to 2020, show that 7570 surgeries related to ankle fractures were performed in Queensland, with a median cost of \$20,653 per admission. Currently an average of 165 surgeries for ankle fractures take place in the Royal Brisbane Womens Hospital (RBWH) per year (for the same period - 2015 to 2020). While these injuries are common and costly, there is little consensus amongst clinicians regarding the best rehabilitation regime. The most recent Cochrane review drew on 38 studies with a total of 1896 participants to conclude there is limited evidence supporting early commencement of weight-bearing and the use of a removeable type of immobilisation to allow exercise during the immobilisation period after surgical fixation (1). That review also concluded that given the risk of adverse events, the patient’s ability to comply with the use of a removeable type of immobilisation to enable controlled exercise is essential, and that there is little evidence for rehabilitation interventions and higher quality studies are needed.

Physiotherapists, orthopaedic surgeons and researchers at the RBWH and the Jamieson Trauma Institute (JTI) have recognised these problems and see the potential to improve the care of patients following surgery for ankle fractures, by streamlining and improving rehabilitation using digital innovations, such as smart orthotics to record weight-bearing, and smartphone apps to record pain scores, adherence to rehabilitation programmes and medication use. A number of these devices have been developed in recent years. For the purposes of this study the Magnes device (Magnes AG, Switzerland) will be used.

Studies to date evidence the important of early weight-bearing and mobilisation(2, 3) but identifying the optimal amount of weight-bearing exercise at different stages of rehabilitation is a recurring challenge in the rehabilitation of patients with ankle fractures (4). At present, clinicians do not have good evidence upon which to base their guidance about when to begin partial or full weight-bearing on their injured leg or other aspects of their rehabilitation protocols (3). As such, the best weight-bearing protocol following ankle fracture surgery, for optimal recovery, is currently unknown.

A further key challenge is that, currently, clinicians are able to monitor patient progress only during face to face or telehealth appointments, therefore gathering evidence of adherence with rehabilitation programs is based on patient recall of activities between appointments.

These challenges are consistent with the preliminary results of our systematic review (in progress) of postoperative rehabilitation of patients with ankle fractures, which shows a lack of evidence to guide decisions about rehabilitation intensity and timing of weight-bearing for optimal fracture healing and functional recovery.

Advances in technology present new opportunities for addressing these issues through remotely tracking patient progress and allowing the clinician to identify the optimal amount of weight-bearing exercise at different stages of rehabilitation, thus reducing reliance on patient recall. In the context of ankle fractures, smart devices may allow real-time gait data capture and in-depth analysis of weight-bearing throughout recovery.

It is anticipated that data gathered through the use of smart technology will help clinicians develop optimal rehabilitation protocols and may also allow for protocols to be delivered without the need for the patient to attend a physiotherapy clinic/specialist rehabilitation setting, offering the opportunity to reduce clinical costs and pressure on waiting lists.

Before a large study testing the added value of smart devices in rehabilitation programmes for those with ankle fracture, a feasibility study is needed to demonstrate that patients are able to use the smart device in their rehabilitation and that the device provides data in ways that can be accessed and potentially used in rehabilitation programmes. This feasibility study aims to evaluate whether patients can use these devices during rehabilitation and whether the data from the device enhance clinical practice. For the purposes of this study, the Magnes device will be used. It is anticipated that findings from this study will be used to inform a larger randomised trial to assess whether adding a weight-bearing and activity recording device during rehabilitation offers additional benefit when compared to standard rehabilitation protocols. In addition, it is anticipated that this feasibility trial will provide valuable insights into patterns of weight-bearing and general physical activity which will be used to help optimise rehabilitation protocols and improve functional outcomes.

2. Study Methods

2.1 Brief summary

The objective of this study is to evaluate the acceptability and feasibility of the Magnes device to monitor weight-bearing and gait characteristics during the rehabilitation phase following surgery for an ankle fracture, from the date of surgery to 12 weeks post-operatively. Alongside the clinical progress of the injured patient, the study will also examine:

1. The recruitment, screening and consent processes for eligible patients entering the study
2. The outcomes used to monitor patient progress up to 12 weeks post-operatively.
3. The acceptability and feasibility of the Magnes device to measure and record weight-bearing and gait characteristics following ankle fracture surgery, from both the patient and clinician perspectives.
4. The accuracy and usefulness of data collected by the Magnes device, for clinical decisions in practice.
5. The feasibility of conducting a future randomised clinical trial using smart devices, which can in turn support the development of new systems to streamline and improve care and outcomes.

It is anticipated that through this process valuable lessons will be learned concerning the methods and procedures above, which will help the development of a larger randomised controlled trial.

2.2 Study Design

This is a single group prospective cohort study, involving patients who have undergone surgical fixation of their unstable ankle fracture with data collection over a period of 12 weeks.

2.3 Interventions

The study will assess acceptance and interaction of patients and clinicians to implementation of a smart device to monitor weight-bearing during the rehabilitation phase following surgery of an unstable ankle fracture. Postoperative rehabilitation will be standardised for the initial 12-week rehabilitation period for all included patients, in accordance with current clinical practice. The patients' weight-bearing and activity will be recorded with the Magnes device.

This study does not examine the effectiveness of surgical or rehabilitation strategies. However, clinical outcomes will be recorded to allow exploration of the correlation between weight-bearing activities, clinical progress and adverse events. The future application of the Magnes device would allow to detect aberrant movement patterns early, hence avoiding complications following ankle fracture fixation.

2.4 Sample Size

A formal sample size calculation is not necessary for the purpose of this feasibility study. Based on the nature of this study, we target a sample size of n=12 patients (5).

2.5 Patient population

Patients will be recruited from the Orthopaedics department at the RBWH in Brisbane, Queensland, Australia. The Orthopaedics department at RBWH performs surgery, on average, on two ankle fractures per week. For the purposes of this feasibility study, it is envisaged that 12 patients will be an adequate sample.

2.6 Participant Recruitment

All patients with a unilateral unstable single malleolar, bi-malleolar and most tri-malleolar fractures requiring surgery, including those with syndesmotic/deltoid ligament injuries, will be approached, screened for contraindications and, if they meet the study inclusion and exclusion criteria (see below) and agree to participate, they will be asked to consent to participation to the study.

Patients will be recruited from the RBWH fracture clinic. The orthopaedic clinic staff will identify the type of fracture and the Charlson Comorbidity Index score before considering the patient for inclusion.

Suitable patients will be identified by the orthopaedics department and contacted by the research nurse in the preoperative phase, so that they are screened for eligibility, informed as to the nature of the study both verbally and by the study pack (which includes an invitation letter, information leaflet explaining the aims and objectives of the study and the consent form) and, if they are suitable for inclusion and agree to take part, sign an informed consent form.

Patients will be informed that they are free to withdraw from the study at any time and that their decision to withdraw will not affect their care in any way. Patients will be obliged to return the smart devices to the research team on completion of, or at the time of withdrawal from, the study.

2.7 Study Eligibility

Patients' eligibility to participate will be determined based on the following inclusion and exclusion criteria.

2.7.1 Inclusion criteria

Patients are eligible to participate in the trial if they:

- Are 18 years or older at the time of recruitment.
- Have suffered an ankle fracture that can be classified as tibia/fibula, malleolar segment (44) according to the AO Foundation-Orthopaedic Trauma Association (AO-OTA) Fracture and Dislocation Classification Compendium 2018 (6):
 - 44-A: infrasyndesmotic fibula injury
 - 44-B: trans-syndesmotic fibula fracture, and
 - 44-C: supra-syndesmotic fibula injuryAnd, had ankle fracture surgery (fracture types include AO-OTA 44-A, 44-B and 44-C; single malleolar, bi-malleolar not extending into the tibial plafond and tri-malleolar with posterior fragment <20%).
- Have a Charlson Comorbidity Index score (7) of 4 or less. (Appendix 3)
- Can stand and walk with and without crutches when wearing the Aircast boot at the time of data collection.
- Can attend follow-up visits at the RBWH in person.

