2.7.2 Exclusion criteria

1. A Charlson Comorbidity Index score 5 or higher
2. Foot or leg size incompatible with available Magnes shoes or Aircast boot
3. Comorbidities:
 - a. concurrent or pre-existing injuries that impair the ability to use the orthosis as intended (e.g. neurological conditions including Multiple Sclerosis, brain injury, spinal cord injury);
 - b. patients with any other disorders involving restriction of mobility, limited ambulation on forearm crutches, or conditions affecting the fracture healing process (e.g. joint disease, neurological disorder, amputation)
 - c. BMI >35kg/m²
4. Require non-standard postoperative care
5. Not able to attend follow-up visits at the RBWH.
6. Have suffered any of the following fracture types:
 - a. talus fractures
 - b. pilon (tibial plafond) fractures
 - c. calcaneal fractures
 - d. stress fractures
 - e. ankle fractures associated with ipsilateral (mid)foot fractures
 - f. bilateral lower limb fractures
 - g. concomitant upper limb fractures or injury
 - h. Posterior malleolus fractures requiring posterior plating
 - i. small and undisplaced fractures that can be managed non-operatively
 - j. trimalleolar fractures with significant posterior involvement that are not suitable for early weight-bearing
 - k. open (compound) fractures or fractures on both lower limbs.

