2.8 Study Intervention

Current practice in the orthopaedic clinics of the RWBH includes fitting all patients operated for an ankle fracture with an Aircast AirSelect Standard walker boot (**Figure 1A**) in the operating theatre. As such, patients will be screened and consented in the pre-operative phase.

The Aircast Airselect Standard walking boot (hereafter referred to as the Aircast boot or Aircast) is shown in Fig. 1A. The Aircast is considered part of standard care for these ankle fracture patients. In clinical practice, the Aircast boot is utilised for fractures of the foot, ankle and distal tibia or fibula, high-grade ankle sprains and for postoperative immobilisation. It offers several advantages over traditional casts such as allowing easier access to the surgical wound, the ability to adjust the Aircast boot depending on swelling and improved durability when used as a walking device.

Those patients who consent to participate in the study will be fitted with the Aircast boot as per usual practice with the addition of a Magnes device attached to the boot, as shown in **Figure 1A**, in the operating theatre following surgical fixation.

[figure not shown]

Figure 1: *The Aircast boot with the Magnes smart device (1A) and the Magnes NUSHU (1B) It has anterior and posterior semi-rigid outer shells that when tightened, using the three straps, immobilises and supports the ankle and provides protection. An inner lining protects the limb from skin irritation. The Aircast has two adjustable distal air cells within the shell that inflate to support the malleoli and provide compression to decrease swelling. The Aircast is available in sizes XS – XL, allowing a suitable fit for most patients.*

In addition, patients will receive a standard information and education leaflet designed for the study (Appendix 1). The information and education leaflet includes information about the smart devices and their care (smart device in the Aircast and the NUSHU shoe) and information on postoperative care (practical guide, weight-bearing, other activities and exercises). This leaflet will facilitate standardisation of the postoperative rehabilitation across patients. (Appendix 1).

Post-operatively patients will be offered up to 6 physiotherapy sessions in fortnightly intervals as per usual practice. (Appendix 2).

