4.0 Data collection

Data will be collected at 2 weeks post-surgery (baseline for this study), and at 6- and 12-weeks follow-up. Non identifiable baseline data, such as gender and age, will be recorded, in addition to non-identifiable health related data, for example, date of injury, injury cause, imaging reports and type of surgery. This information will be recorded on a secure, password protected Metro North REDCap server. See Appendix 5 for a pdf of the REDCap data dictionary. Range of movement, AFORM and EQ-5D 5L: measures will be taken at each follow-up visit.

Table 1: Outcomes to be recorded at patient follow-up visits

No.	Measurement	Description	When measured
Ability to use technology: insoles and iPad App			
1.	Data upload	Has the data been uploaded to the cloud successfully for the time period in question	2, 6, 8, 10 and 12 weeks
2.	Device charging and monitoring	How long each day did the patient wear the boot/shoe? Did the device remain charged (and able to record data) for the time period in question? Were there any problems related to keeping the battery charged?	2 weeks, 6 weeks, 12 weeks
3.	Other issues raised by the patient	Description of any other problems faced by the patient that limit their ability to use the device and capture data.	2 weeks, 6 weeks, 12 weeks
4.	Ownership of a smartphone	Patients will be asked if they own a smartphone (necessary as the future randomised trial will require this)	At recruitment
Patient Reported Outcome Measures			
5.	AFORM	Standardised questionnaire, filled in by the patient.	2, 6 and 12 weeks
6.	EQ-5D 5L: EuroQol five-dimension health utility tool	Standardised questionnaire, filled in by the patient.	2, 6 and 12 weeks
7.	Return to work	Has the patient returned to work? Is the patient able to return to work?	2, 6 and 12 weeks
8.	Medication review	Consumption of OTC and prescription analgesics	Daily for 12 weeks
Other clinical measures			
9.	X-ray ankle	XR ankle: WB out of cast – AP/lateral/mortise	6 weeks
10.	Wound review	Orthopaedic Department Nurse	2 weeks
11.	Weight-bearing	Magnes Sensor Data	2-6 -8*-12 weeks

No.	Measurement	Description	When measured
12.	Complications	Orthopaedic Department Nurse	Throughout the duration of the project
Range of Motion Measures			
13.	Ankle dorsiflexion (DF)	Measured using a standard goniometer	2, 6 and 12 weeks
14.	Ankle dorsiflexion (DF) (knee to wall)	Measured using a standard ruler	2, 6 and 12 weeks

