APPENDIX 1: Rehabilitation protocol

Ankle Fracture - Post operative Physiotherapy

The following is a guide only, please check for any changes or variances as indicated by your surgeon's post-operative plan.

(Excludes tibial plafond fractures and large posterior malleolar fractures)

0 to 2 weeks Gentle walking and elevation PWB

- Physiotherapy review post operatively for crutches
- Apply air-cast boot in theatre after surgery – No inflation
- **PWB (partial weight bear)** in air-cast boot with crutches is ok
You may opt to NWB (non-weight bear) due to pain, this is ok too.
After 3-5 days start to try and take some weight (<50% of your weight) on your

foot with the boot

- Keep boot on at all times - leave on 24/7 but check your skin underneath by undoing daily to view your skin by removing the front panel
- Rest and elevate to allow for wound healing – aim to keep your leg elevated 23hrs/day
 - When sitting elevate your leg on a foot stool, chair or up on sofa
 - When lying down, you can elevate your leg on a single pillow
 - Don't walk too much, aim for essential walking within your home in the first week
- Do not get dressings wet – cover your lower leg in a cast bag for showering
- Leave dressings intact for 10-14 days - until the '2 week' follow up
- Around 2 weeks you will have dressing removed and wound reviewed by a doctor
- A tubi-grip will be applied and the air-cast boot re-applied
- Teach application of air-cast boot – **but not to inflate for first 2weeks** and until dressing removed

Video demo: <https://www.youtube.com/watch?v=XnBm68oTDOw>

Crutches PWB = Partial Weight Bear

= <50% of your body weight

Boot on at all times

- Aim for ankle in neutral (90°)
- Can be refitted if needed to ensure heel down
- Or to check skin condition daily.

[figure not shown]
Walking with crutches:

- Crutches in front first, boot foot next taking **Partial weight** as pain allows (**up to 50% of your body weight**), good foot follows stepping up to (not past) operated foot (can use scales to check weight you're

2 to 6 weeks Progress more weight onto foot and start ankle movement WBAT

WBAT (weight bear as tolerated = up to full weight) in air-cast boot with crutches, boot inflated

- Boot on for all walking using 2 crutches
- You may be able to manage with 1 crutch indoors (crutch in opposite hand to foot)
- If painful or limping continue with 2 crutches
- Aim for step-through gait – Physiotherapist to review and advise

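### The inclusion criterion on walking in the Aircast boot cannot be judged at pre-operative screening, and it disagrees with the synopsis and with the crutch schedule in Appendix 1

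*Protocol*

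**What the plan says.** The criterion is the fourth in protocol section 2.7.1: "Can stand and walk with and without crutches when wearing the Aircast boot at the time of data collection". The synopsis lists a different one: "Can stand and use crutches post operatively".

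Section 2.6 says that suitable patients are "contacted by the research nurse in the preoperative phase, so that they are screened for eligibility", and that they sign consent if suitable and willing. Section 2.8 repeats the timing: "As such, patients will be screened and consented in the pre-operative phase". After fixation, in theatre, the usual boot is fitted "with the addition of a Magnes device attached to the boot".

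Section 4.0 sets the collection times: "Data will be collected at 2 weeks post-surgery (baseline for this study), and at 6- and 12-weeks follow-up".

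For weeks 2 to 6, Appendix 1 states: "Boot on for all walking using 2 crutches". The next line allows that one crutch may be enough indoors. Walking without crutches comes in the weeks 6 to 8 block, as the last step of weaning from the boot. Sections 2.8 and 3.2.1 replace the boot by the NUSHU shoe at about week 6, depending on healing.

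A related entry in section 2.7.2 excludes patients who "Require non-standard postoperative care".

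**The concern.** An eligibility criterion has to be answerable when the patient is enrolled. This one refers to walking in a boot that has not yet been fitted, at a time after the operation. Section 2.7.1 ties age to the time of recruitment, so the later time point here changes the meaning.

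Two things are at stake. First, staff cannot apply the rule as written, in a study that lists its own recruitment and screening process among the things to be examined (section 2.1). Second, a rule judged after fitting could be used to reclassify a patient as ineligible because of how he or she walked in the instrumented boot. Aim 1 in section 3.1 concerns weight-bearing in that boot, so such a patient carries information about feasibility. Losing even one of 12 would show in the summaries that are meant to inform the randomised trial.

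**Working it through.** **Step 1. Timing, with the sections side by side.**

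| Time | Protocol text | Can the criterion be judged? |
|---|---|---|
| Before surgery | Screening and consent (2.6, 2.8) | No; no boot is worn |
| In theatre | Boot and device fitted (2.8) | No |
| Weeks 0 to 2 | Partial weight-bearing in the boot with crutches; no weight-bearing is also allowed (Appendix 1) | The part without crutches is not in the leaflet |
| Week 2 visit | First clinic data collection (4.0); section 3.2 has partial weight-bearing begin after this visit | The part without crutches is not met |
| Weeks 2 to 6 | Two crutches in the boot, one possible indoors (Appendix 1) | The part without crutches is not met |
| Weeks 6 to 8 | Full weight-bearing out of the boot, from crutches to one to none; boot still worn outdoors until week 8 (Appendix 1) | Possible late in this window |
| Week 12 visit | NUSHU shoe in use (2.8) | No longer applies; the boot has been replaced |

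The criterion cannot be checked when eligibility is decided. A patient following the leaflet does not satisfy its literal wording at the first data-collection visit. At the last visit it refers to footwear no longer in use.

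The table also shows that section 3.2 and Appendix 1 differ on when partial weight-bearing starts. This matters here because the criterion must agree with whichever text stands.

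**Step 2. What happens to a patient who fails it later.** No section says that such a patient is removed, replaced or reclassified. Section 5.0 has reasons for withdrawal or dropout recorded and stops further data collection. The REDCap completion form in Appendix 5 offers non-compliance, not wishing to continue, or other; it has no entry for ineligibility. Removal is neither required nor ruled out.

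**Step 3. How much a removal could matter.** There is no figure in the plan to reproduce: section 2.4 sets n = 12 without a formal calculation. The following is illustrative. The number affected (k) is assumed, and a proportion of patients succeeding is used only as a yardstick, since section 3.1 lists no such endpoint. With all patients kept the proportion is (12 − k)/12; with the k patients removed it is (12 − k)/(12 − k). The exact 95% limits are beta quantiles: lower B(0.025; x, n − x + 1), upper B(0.975; x + 1, n − x).

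| k (assumed) | All kept | k removed |
|---|---|---|
| 1 | 11/12 = 91.7% (61.5 to 99.8) | 11/11 = 100% (71.5 to 100) |
| 2 | 10/12 = 83.3% (51.6 to 97.9) | 10/10 = 100% (69.2 to 100) |
| 3 | 9/12 = 75.0% (42.8 to 94.5) | 9/9 = 100% (66.4 to 100) |
| 4 | 8/12 = 66.7% (34.9 to 90.1) | 8/8 = 100% (63.1 to 100) |

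If two further patients fail for another reason and stay in, k = 3 gives 7/12 = 58.3% against 7/9 = 77.8%.

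The chance that at least one of 12 is affected is 1 − (1 − p)^12. For assumed p of 5%, 10%, 20% and 30% this is 46%, 72%, 93% and 99%.

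**The case against.** The strongest reply is that this is loose wording with no stated consequence. Several parts of that reply stand.

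- **Removal is not prescribed.** A reader might infer that patients in whom the device fails will be dropped as ineligible. The documents do not support that. Nothing orders removal, and the criterion tests walking in the boot, which is standard care. Lost charge, failed upload or a device-related adverse event makes nobody ineligible under it. Inability to walk without crutches may reflect only the injury.
- **The analysis set may be defined elsewhere.** A statistical analysis plan, not shown here, may settle which fitted patients are counted. The lack of a denominator rule is therefore not the finding.
- **The percentages are illustrative.** Section 3.1 lists weight-bearing, charge, adverse events, upload and interviews, with no proportion of successful users and no threshold.
- **The crutch conflict has limits.** Appendix 1 calls itself a guide, allows one crutch indoors in weeks 2 to 6, and keeps the boot outdoors until week 8. The sensor also records from surgery, so data collection need not mean the week 2 visit. Walking in the boot both with and without crutches could occur at some point under the leaflet.
- **Exclusion 4 is partly foreseeable.** A reader might infer that non-standard postoperative care is known only after surgery. Fracture type and history, which section 2.7.2 also uses, can indicate it beforehand.

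What does not stand is the suggestion that the criterion can be left alone. On any of these readings it refers to a time after enrolment and differs from the synopsis. An analysis plan cannot make it assessable before surgery.

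**Conclusion.** The point holds as a fault in the eligibility text. The criterion cannot be applied when eligibility is decided, it differs from the synopsis, and read literally it is not met at week 2 by a patient who follows Appendix 1. This rests on the protocol wording alone.

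The effect on the results is a possibility only. It requires that someone is declared ineligible after fitting because of walking ability, and the protocol gives no rate from which to estimate how often that would arise. With 12 patients, each such removal from a simple count of the kind illustrated would raise the apparent result by several percentage points or more.

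In a single-group study of this size, without an effectiveness claim, this is something that should be fixed rather than a fatal flaw.

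**What to change.** 1. Restate the criterion so that the research nurse can judge it at pre-operative screening, and use identical text in the synopsis and section 2.7.1.
2. Have the sponsor reconcile it with the crutch and weight-bearing passages in section 3.2 and Appendix 1. No view is taken here on which clinical rule is right.
3. Add a sentence that a consented patient fitted with the device is not made ineligible by later walking ability or by a later move to non-standard care. Such a patient stays in the feasibility summaries, and the event is reported as an outcome with its reason.

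The cost is a short amendment to the eligibility text and one added sentence. The downside is that the feasibility results may look slightly less favourable.
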